9.4 Statistical Evaluation of Primary Endpoint

9.4.1 Statistical Hypotheses:

The specific null and alternative hypotheses for comparing these two treatments in a non-inferiority design are: $H_0: \pi_{LDV/SOF+ribavirin} - \pi_{LDV/SOF} = \delta_0$ and $H_A: \pi_{LDV/SOF+ribavirin} - \pi_{LDV/SOF} < \delta_0$ (non-inferior) where $\delta_0 = 0.10$. where $\pi_{LDV/SOF+ribavirin}$ (assumed to be 95%) represents the proportion with a successful outcome due to treatment with LDV/SOF plus ribavirin for 12 weeks and $\pi_{LDV/SOF}$ represents the proportion of a successful outcome due to treatment with LDV/SOF for 12 weeks.

9.4.2 Efficacy Analysis:

Although there is insufficient power to conduct any formal statistical analyses, preliminary estimates of effects for treatment comparisons will be intent-to-treat, where all randomized subjects will be included in the analysis and each subject will be included in the treatment to which they were randomized.

Baseline demographics and clinical outcomes will be presented by treatment. Estimates of the differences between these, along with 95% confidence intervals, will be generated. The primary outcome of proportion of subjects with success (defined as the proportion of subjects achieving sustained virologic response 12 (SVR12) weeks after completing the antiviral regimen) as well as estimates of all secondary outcomes for each treatment will be reported along with 95% confidence intervals.

9.7 Safety Analysis

9.7.1 Safety Outcomes

Safety outcomes include the proportion of subjects who experience any treatment-related serious adverse events (SAEs) during the treatment phase and up to 30 days following completion of the treatment.

Overall safety and tolerability of each regimen will be estimated by measuring the incidence of:

- Development of medication intolerance requiring dose reduction, temporary withdrawal, or removal of the study drug(s)
- Incidence of the need for supportive medications (erythropoietins, colony-stimulating factors)
- Incidence of intolerance requiring dose reduction, temporary withdrawal, or removal of immunosuppressants
- Overall and opportunistic infections
- Biopsy-proven rejection rates
- Mortality
- Graft loss

Other specific SAEs to be monitored may be added in consultation with the DSMB. The cumulative incidences of each outcome will be estimated along with 95% confidence intervals.

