3. STUDY DESIGN

Multi-center, prospective, randomized, open-label, pilot study

ARM 1: LDV/SOF x 12 weeks

ARM 2: LDV/SOF + RBV x 12 weeks

Number subjects:

Multi-center

50 subjects, with 25 subjects in each arm

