9.2 Outcomes

9.2.1 Primary outcome - Treatment efficacy, defined as the proportion of subjects achieving sustained virologic response 12 (SVR12) weeks after completing the antiviral regimen

9.2.2 Secondary outcomes - Secondary endpoints include the proportion of subjects achieving clearance of viremia during therapy, at the end of therapy, week 4 and 24 SVR (week 4, week 8, EOT, SVR4, SVR24).

9.2.3 Safety outcomes - Overall safety and tolerability of each regimen will be estimated by measuring the incidence of adverse drug reactions and the development of medication intolerance requiring dose reduction, temporary withdrawal, or removal of the study drug(s), incidence of the need for supportive medications (erythropoietins, colony-stimulating factors), incidence of intolerance requiring dose reduction, temporary withdrawal, or removal of immunosuppressants, overall and opportunistic infections, biopsy-proven rejection rates, death, and graft loss. Other safety outcomes include virologic mutations based on NS5A and NS5B viral substitutions at baseline and in the event of virologic failure.

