9.7.2 Interim Safety Monitoring

The Data Safety Monitoring Board (DSMB) will review study safety event rates, center performance, adverse events (AEs), and serious adverse events (SAEs) periodically. This review will identify any clinical, operational, or other data issues that might require changes or adjustments in the way in which the trial is conducted as well as any safety issues that may need to be addressed. In order to accommodate this, the Data Coordination Unit (DCU) will generate safety monitoring reports as well as a comprehensive statistical report periodically for the DSMB. These reports will contain compiled data on enrollment, demographic and baseline characteristics, eligibility and protocol violations, safety data, concomitant medications and procedures, and data quality (e.g., timeliness of data entry, and number of data clarification requests generated and resolved). All AEs and SAEs will be coded using MedDRA and summarized in terms of frequency of the event, number of subjects having the event, timing relative to randomization, and severity and relatedness to treatment. For each review, the DCU will generate two statistical reports – an open, blinded report to be distributed to the Executive Committee and the DSMB, and a closed report to be distributed only to the DSMB. For the closed report only, the statistics will also be provided by partially blinded treatment group (A vs B). If the DSMB wishes to be completely unblinded for closed reports, a sealed treatment identification envelope will be provided to the DSMB; this envelope can be opened at the discretion of the DSMB. The closed report will also contain data listings identifying subjects with specific safety outcomes such as mortality.

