10.4 Adverse Experience Reporting

In order to ensure prompt reporting of adverse events, all adverse events (as well as all related study data) must be entered into the WebDCU™ within five days of collection date. All serious adverse events (SAEs) must be reported on the WebDCU™ within 24 hours of the study site staff first being made aware of its occurrence. The site investigators are required to provide relevant information, including description of the adverse event, date/time of onset and resolution, severity and seriousness, action taken, and suspected relationship to the study treatment.

Reporting of any serious adverse event will trigger notification of the event to the DCU Project Manager (PM) and the independent Medical Safety Monitor (MSM). The MSM will conduct an independent review of each of these events to determine if it is serious, unexpected, and study treatment related.

Periodically throughout the study, the MSM will review reports on the incidence rates of all reported adverse events, whether serious or not. Should such monitoring uncover issues that may threaten subject safety (e.g. unexpectedly high rate of adverse events), the study statistician and principal investigator will prepare a report to be submitted to the DSMB for their review and further actions to be taken, if any.

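### The only named SAE outcome counts treatment-related events alone in an open-label trial; an all-cause SAE proportion by arm should stand beside it

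*Combined protocol and SAP*

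**What the plan says.** Section 9.7.1 lists among the safety outcomes the share of subjects with "any treatment-related serious adverse events (SAEs"), counted "during the treatment phase and up to 30 days following completion of the treatment". It then gives a separate list for overall safety and tolerability: study-drug intolerance leading to dose change or withdrawal, supportive medications, immunosuppressant intolerance, infections, biopsy-proven rejection, mortality and graft loss. Cumulative incidences are to be reported with 95% CIs. Section 9.2.3 has nearly the same components and opens with "measuring the incidence of adverse drug reactions", which is also an attribution term.

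Section 3 describes a "Multi-center, prospective, randomized, open-label, pilot study". The arms differ only in ribavirin: "ARM 2: LDV/SOF + RBV x 12 weeks" against LDV/SOF alone for the same duration. Section 2.1 describes ribavirin as poorly tolerated after transplant and names a ribavirin-free regimen as one of the main open questions.

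Under section 10.4 the site investigator records the suspected relationship of each event to study treatment. An independent Medical Safety Monitor then reviews each SAE "to determine if it is serious, unexpected, and study treatment related". Neither assessment is said to be masked to arm, and no rule says which of the two defines the 9.7.1 outcome.

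Section 9.7.2 has all AEs and SAEs summarised for the DSMB, including by "severity and relatedness to treatment". Statistics by coded arm appear only in the closed report, which goes only to the DSMB.

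**The concern.** Whether an SAE occurred is largely a matter of fact; whether it was related to treatment is a judgement. Here the judgement begins with a site investigator who knows the arm. Section 7 also gives that investigator a separate table of events expected with ribavirin, including anemia, hemolysis, hepatic failure, pancreatitis, dyspnea, low neutrophils and depression. Some of these can also arise as background events after transplant. In Arm 2 such an event has a drug explanation listed in the protocol; in Arm 1 the same event is not on the list common to both drugs. Arm 2 also has more study drugs to which an event can be attributed. The label may therefore not mean the same thing in each arm.

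The likely direction is more related SAEs in Arm 2, which would make the ribavirin-free regimen look safer. That is the contrast the trial is meant to inform, and the pilot's stated purpose is estimation. A shift in the measure would carry into the estimates taken forward.

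**Working it through.** The plan gives no expected SAE rate and no attribution share, so there is no figure of its own to reproduce. The sample-size statement in section 9.3 concerns SVR12 and has no bearing here. The check has three parts.

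**1. Is an all-cause SAE proportion by arm named anywhere as an outcome?**

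- 9.2.3: adverse drug reactions and a list of specific events; no all-cause SAE or AE proportion.
- 9.7.1: treatment-related SAEs and a list of specific events; no all-cause SAE proportion.
- 9.7.2: all AEs and SAEs, related or not, but as content of periodic DSMB reports.

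It is therefore not a named outcome of the final analysis.

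**2. How far could attribution alone move the comparison?**

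All rates here are assumptions; none comes from the documents. Let s be the all-cause SAE proportion, equal in both arms, and let a1 and a2 be the shares called related in Arms 1 and 2. With at most one SAE per subject:

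related proportion in arm k = s × a_k; apparent excess = s × (a2 − a1).

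Take a1 = 30% and a2 = 50% or 70%:

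| s (both arms) | Arm 1, a1 = 30% | Arm 2, a2 = 50% | Arm 2, a2 = 70% | Apparent excess |
|---|---|---|---|---|
| 10% | 3% | 5% | 7% | 2 to 4 points |
| 20% | 6% | 10% | 14% | 4 to 8 points |
| 30% | 9% | 15% | 21% | 6 to 12 points |

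The true all-cause difference is 0 in every row. With a1 = a2 = 30% the apparent excess is also 0, so the whole effect comes from unequal attribution. With 25 subjects per arm (section 3), 2 points is 0.02 × 25 = 0.5 subject and 12 points is 0.12 × 25 = 3 subjects.

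For scale, an observed 3/25 has an exact 95% CI of 2.5% to 31.2%. A comparison of 3/25 with 1/25 is a difference of 8 points, with a Newcombe 95% CI of about −9 to 26 points.

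**3. Are the data for an all-cause line already collected?**

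Section 10.4 requires every AE and SAE to be entered, whatever its relatedness. Section 6.1 requires AE review at each scheduled visit from Week 4, including Weeks 16 and 24. Treatment ends around Day 84, so the 30-day window closes around Day 84 + 30 = 114. The Week 24 visit (Day 168) lies beyond that, so the window is covered.

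**The case against.** The strongest reply is that the plan's safety assessment is much broader than this one proportion. A reader might infer that the whole tolerability contrast rests on attribution. The documents do not support that. Supportive medications, infections, biopsy-proven rejection, mortality and graft loss in 9.7.1 need no relatedness call. The two intolerance items do involve judgement. A reader might also take related SAEs to be the leading safety outcome, but 9.7.1 only says that safety outcomes include them and sets no ranking.

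Second, an independent monitor reviews each SAE, and all events are summarised for the DSMB. Both reduce the concern. But independence is not masking, and the DSMB summary is not a final-analysis outcome. The documents are silent on masking, so it would be equally wrong to state that the monitor will be unmasked.

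Third, unequal attribution is not necessarily bias. Arm 2 receives an extra drug, and a larger share of its SAEs may truly be caused by treatment. This stands. The table shows what attribution alone could do, not what it will do.

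Fourth, all-cause SAEs have their own weakness: background post-transplant events enter both arms, add noise and may dilute a true ribavirin effect. This also stands, and it argues for reporting both lines rather than replacing one with the other.

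Finally, section 9.7.3 sets its 10% level on related SAEs, so a reader might infer that the stopping provision is distorted too. Unequal attribution would reach it, but that provision is discretionary and arises on DSMB concern. Adding an outcome to 9.7.1 would not change it, so no claim about stopping is made here.

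**Conclusion.** The point holds as a limited one. The only SAE proportion named for the final analysis depends on a relatedness judgement that is not stated to be masked, in an open-label comparison of adding a drug expected to be poorly tolerated. Under the assumed rates, attribution alone could produce an apparent excess of 2 to 12 percentage points in Arm 2. That range rests on equal all-cause rates of 10% to 30%, attribution of 30% against 50% to 70%, and one SAE per subject. At 25 per arm such shifts lie within sampling error. Low precision does not make a measure that shifts with knowledge of the arm a better one, particularly when its estimates are meant to inform a later trial. This is a cheap improvement to reporting, not a flaw that undermines the safety analysis.

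**What to change.** - **Section 9.7.1:** add the proportion of subjects with any SAE regardless of relatedness, from treatment start to 30 days after treatment, by arm with a 95% CI. Report it beside the treatment-related proportion. State whether the site investigator's or the Medical Safety Monitor's relatedness call defines the related line, and whether that call is masked to arm.
- **Section 9.2.3:** report all-cause AEs beside adverse drug reactions.

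The cost is a few lines of wording and an extra table row for SAEs, with a matching one for AEs. No new data are needed. Because the all-cause line includes background post-transplant events, neither line should be read without the other.

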9.7.2 Interim Safety Monitoring

The Data Safety Monitoring Board (DSMB) will review study safety event rates, center performance, adverse events (AEs), and serious adverse events (SAEs) periodically. This review will identify any clinical, operational, or other data issues that might require changes or adjustments in the way in which the trial is conducted as well as any safety issues that may need to be addressed. In order to accommodate this, the Data Coordination Unit (DCU) will generate safety monitoring reports as well as a comprehensive statistical report periodically for the DSMB. These reports will contain compiled data on enrollment, demographic and baseline characteristics, eligibility and protocol violations, safety data, concomitant medications and procedures, and data quality (e.g., timeliness of data entry, and number of data clarification requests generated and resolved). All AEs and SAEs will be coded using MedDRA and summarized in terms of frequency of the event, number of subjects having the event, timing relative to randomization, and severity and relatedness to treatment. For each review, the DCU will generate two statistical reports – an open, blinded report to be distributed to the Executive Committee and the DSMB, and a closed report to be distributed only to the DSMB. For the closed report only, the statistics will also be provided by partially blinded treatment group (A vs B). If the DSMB wishes to be completely unblinded for closed reports, a sealed treatment identification envelope will be provided to the DSMB; this envelope can be opened at the discretion of the DSMB. The closed report will also contain data listings identifying subjects with specific safety outcomes such as mortality.

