2. BACKGROUND

2.1 Rationale

Therapeutic response rates for the treatment of recurrent hepatitis C virus (HCV) after liver transplant have historically lagged behind non-transplant patients (1). While the latest studies in HCV therapy with new direct-acting antivirals (DAA) have drastically improved sustained virologic response rates (SVR) in non-transplant patients, HCV is still the most common cause of end stage liver disease (ESLD) leading to liver transplant (2,3,4,5). Although the DAAs have shown efficacy in recurrent HCV post-transplant, this is with late treatment, since preemptive therapy has not shown benefit with previous agents (6,7). An attempt at preventing recurrence by clearing the virus with SOF and RBV prior to transplant has shown encouraging preliminary results in patients who had HCV RNA undetectability for ≥ 30 days, however this was in well-compensated cirrhotics ($CTP \leq 7$) with concomitant HCC (8). Due to the poor tolerability of RBV in patients with more advanced cirrhosis, it is unknown if this regimen would have external validity to the overall HCV population awaiting liver transplant. Also complicating the reproducibility of this data is the unpredictable timing of liver transplant surgery.

[figure not shown]
Preliminary results of the ongoing SOLAR-1 study have shown excellent sustained virologic response (SVR) rates with 12 weeks of therapy both pre and post-transplant, when utilizing a regimen of LDV/SOF and RBV (9). However, this is with a regimen that includes an antiviral with poor tolerability post-transplant, ribavirin.

The predominant remaining questions for post-transplant treatment of HCV in the DAA era are whether a ribavirin-free regimen is possible and whether pre-emptive treatment is now a potential option to prevent long-term damage to the allograft.

These questions require formal testing in a clinical trial conducted in transplant centers.

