9.7.3 Stopping the Trial Based on Interim Safety Data

In case of concern for safety issue arises from DSMB, the trial may be stopped temporarily or permanently if the serious adverse event rate (SAEs related to the study treatment) exceeds a clinically acceptable rate of 10% in either arm. Data for events will not be evaluated until the first 30 subjects have completed 30 day post treatment follow-up for each arm.

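### No by-arm summary of virologic failure is specified for the DSMB, and the only monitoring criterion is the related-SAE rate

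*Combined protocol and SAP*

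**What the plan says.** Section 9.7.2 sets the DSMB's task: "The Data Safety Monitoring Board (DSMB) will review study safety event rates, center performance, adverse events (AEs), and serious adverse events (SAEs) periodically". It then itemizes the reports: "These reports will contain compiled data on enrollment, demographic and baseline characteristics, eligibility and protocol violations, safety data, concomitant medications and procedures", followed by data quality. Statistics by arm appear only in the closed report, as A versus B, with an envelope if the DSMB wants full unblinding.

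Section 9.7.1 lists the safety outcomes: related SAEs, intolerance, supportive medication, changes to immunosuppression, infection, rejection, mortality and graft loss. Virologic failure is not among them.

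Section 9.7.3 has one criterion. The trial may be stopped if the "serious adverse event rate (SAEs related to the study treatment) exceeds a clinically acceptable rate of 10% in either arm". It adds: "Data for events will not be evaluated until the first 30 subjects have completed 30 day post treatment follow-up for each arm".

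Section 8 defines breakthrough, rebound, nonresponse and relapse, and with section 6.2.3 it says what happens to the individual subject. Neither section calls for a count by arm.

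**The concern.** The arms differ only in ribavirin. Section 2.1 frames the question: "The predominant remaining questions for post-transplant treatment of HCV in the DAA era are whether a ribavirin-free regimen is possible". The post-transplant efficacy data in section 2.2 come from LDV/SOF given with ribavirin, and section 9.4.1 sets the hypothesis around a 10-point loss of SVR12 without it. Loss of efficacy in Arm 1 is therefore the outcome the hypothesis is built to address.

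The monitoring looks elsewhere. Section 2.1 describes ribavirin as poorly tolerated after transplant, so a related-SAE criterion mainly watches Arm 2. Arm 1 could look favorable on SAEs while more of its subjects fail virologically, and nobody is assigned to compare failures between arms. Each site sees its own cases; the coordinating unit compiles data across sites, but the specified report does not ask for this item.

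**Working it through.** **Inputs.** 25 subjects per arm (section 3). Assumed SVR12 95% and margin 10 points (sections 9.3 and 9.4.1), so failure is 5% as assumed and 15% at the margin. Failure rates of 20% and 25% are illustrative and not in the documents. HCV RNA is required at baseline and Weeks 4, 8, 12, 16, 24 and 36, that is days 28, 56, 84, 112, 168 and 252 (section 6.1).

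**The plan's own figure.** With one-sided 0.025 and 80% power, n per arm = (1.960 + 0.842)² × 2 × 0.95 × 0.05 / 0.10² = 7.85 × 0.095 / 0.01 = 74.6, so 75. This matches section 9.3 and confirms how the 95% and the 10-point margin are used.

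**Expected failures in an arm of 25.** 25 × 0.05 = 1.25; 25 × 0.15 = 3.75; 25 × 0.25 = 6.25. The plan specifies no report in which the DSMB would see any of these counts by arm.

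**When the data exist.** On-treatment failure can show in the scheduled tests up to day 84, relapse from day 112, and SVR12 at day 168 (84 + 84). Section 10.1 has clinical data entered in real time. No new test is needed.

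**What a mid-trial count could show.** Take 12 subjects of one arm with follow-up to about day 168, and treat 1 minus SVR12 as the failure rate p. Then P(3 or more) = 1 − Σ C(12,x) pˣ (1−p)¹²⁻ˣ over x = 0, 1, 2.

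| True SVR12 | p | P(0) + P(1) + P(2) | P(3 or more of 12) |
|---|---|---|---|
| 95% | 0.05 | 0.540 + 0.341 + 0.099 | 2% |
| 85% | 0.15 | 0.142 + 0.301 + 0.292 | 26% |
| 80% | 0.20 | 0.069 + 0.206 + 0.283 | 44% |
| 75% | 0.25 | 0.032 + 0.127 + 0.232 | 61% |

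**The full arm.** P(4 or more of 25) is 3%, 53%, 77% and 90% at the same four rates. By then all 25 have been randomized.

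**Cost of using both checks.** At 95% SVR12, the chance that 3 or more of the first 12 fail, or 4 or more of all 25, is 4.3% in one arm. For at least one of two arms it is 1 − (1 − 0.043)² = 8.4%.

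**The existing criterion.** 30 subjects in each arm means 60, and section 3 plans 50. Read per arm, the SAE criterion could never be evaluated. If 30 means both arms together, about 15 per arm would be needed, each followed for about 84 + 30 = 114 days.

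**The case against.** The strongest reply is that the DSMB is not blind to virology. Section 9.2.3 says: "Other safety outcomes include virologic mutations based on NS5A and NS5B viral substitutions at baseline and in the event of virologic failure". Safety data go to the DSMB by arm, section 9.7.2 promises a comprehensive statistical report, and the remit extends to other clinical data issues. Graft loss, which section 8 counts as a treatment failure, is a listed safety outcome. The trial is open-label, and each failure is confirmed and acted on.

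Much of this stands. A reader might infer that the DSMB receives no virologic data at all, or that an excess of failures cannot be seen. The documents do not support either reading: what is missing is a specified summary, and the DSMB could ask for one. The reply does not supply that summary, however. Section 9.7.1 leaves substitutions out of its list, the schedule marks post-baseline substitution testing optional (section 6.2.3 requires it at end of treatment on virologic failure), and a listing of substitutions is not a failure count with a denominator.

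A second reply is that this is a 50-subject pilot which section 9.4.2 says lacks power for formal analysis, so an efficacy trigger is a matter of preference. That stands against a numeric trigger. It does not stand against a descriptive table.

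Third, section 6.2.3 allows alternative treatment after virologic failure, with drug support on request, which limits the harm to the individual subject. That is true, but it does not inform anyone about the arm.

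**Conclusion.** The point holds as a cheap improvement. A DSMB served exactly as section 9.7.2 specifies would have no failure count by arm, although loss of efficacy without ribavirin is what the trial's hypothesis concerns. Nothing in the documents is contradicted by this omission.

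Three limits apply.

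- A reader might take the probabilities for 25 subjects as protection while subjects are still being randomized. They describe a fully enrolled arm and give none. The figures for 12 subjects are the relevant ones, and they show that a mid-trial check would usually miss an excess at the margin (26%).
- Those figures equate failure with 1 minus SVR12 and assume follow-up to about day 168. Under intent-to-treat, non-SVR may also include death, loss to follow-up or never being dosed, and an earlier look sees only part of the failures.
- No accrual rate or duration is given, so the benefit during enrollment cannot be sized. If enrollment closed within about 16 to 24 weeks, relapse and SVR12 data would come too late to affect it. The table could still inform the DSMB about subjects on treatment or in follow-up.

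That failure is the main risk of dropping ribavirin is an inference a reader might draw from the hypothesis; no section says so.

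**What to change.** In section 9.7.2, add one table to the closed report, cumulative and by arm (A versus B): number treated; on-treatment virologic failures, split into breakthrough, rebound and nonresponse; relapses; and HCV RNA status at Weeks 4, 8, 12, 16 and 24. All of it comes from data already collected.

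A non-binding review prompt on failure counts is optional and for the DSMB and sponsor to decide. If one is used, state its operating characteristics at the interim sample size, as in the table for 12 subjects, and give the combined false-trigger chance over all looks and both arms.

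In the same edit, reconcile the wait in section 9.7.3 for 30 subjects in each arm with the 25 per arm in section 3.

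The cost is wording in the protocol or DSMB charter, one more closed-report table, and interim arm-level efficacy data seen by the DSMB only.
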